5.4.2 Data Collection and Follow-up for Withdrawn Subjects

If a Participant withdraws from the study, no additional attempts will be made to contact the Participant.

6 Study Drug

6.1 Description

Nucala (mepolizumab) is a humanized IL-5 antagonist monoclonal antibody. It is expressed in a recombinant Chinese Hamster Ovary (CHO) cell line.

Nucala is supplied as a sterile, white to off-white, preservative-free, lyophilized powder for subcutaneous injection after reconstitution. Upon reconstitution with 1.2 mL of Sterile Water for Injection, the resulting concentration is 100 mg/mL and delivers 1 mL.

6.2 Treatment Regimen

All study participants will receive Nucala 200 mg SQ at week 0, 2,4,6, and 8 for a total of 5 injections.

6.3 Method for Assigning Subjects to Treatment Groups

This is an open-label pilot investigation and all study participants are assigned to active treatment. There is no placebo arm in this study.

6.4 Preparation and Administration of Study Drug

The study drug will be stored and dispensed at each study visit from the Mayo Clinic Research Pharmacy in Florida.

6.5 Subject Compliance Monitoring

Study participants will receive Nucala subcutaneous injection at each follow-up visit.

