3.1 General Description

This is an open-label, single arm exploratory study of mepolizumab in the treatment of CSU. The primary endpoint will be the mean reduction in the seven day urticaria activity score (UAS7) before and after 10 weeks of treatment with mepolizumab. Secondary endpoints will be the mean

reduction of the urticaria control test (UCT) score and the weekly itch severity score (ISS) before and after treatment. Enrollment examination will include a standardized history and examination, baseline UCT score, CBC with differential, serum IgE level, chronic urticaria index, IgE Fc receptor antibody functional assay, and a 4 mm punch biopsy of lesional skin. Patients will discontinue all anti-histamines and start cetirizine 10 mg PO BID which will be continued throughout the study duration. Patients will be provided with a log book to track daily urticaria signs and symptoms in a standardized manner for UAS scoring. At week 0 (enrollment visit +7 days), baseline UAS7 and ISS score will be assessed and skin biopsy results reviewed. Patients with a confirmatory skin biopsy will receive 200 mg SC of mepolizumab at week 0,2,4,6, and 8. UAS-7 and weekly ISS score will be calculated at week 0, 4, 8, and 10. UCT scoring will be calculated at week 0 and at week 10. Repeat CBC with differential, serum IgE level, and measures of basophil serum activation (chronic urticaria index, IgE FC Receptor antibody functional assay) will be assessed at week 10. Attached to this document is a protocol summary.

4 Number of Subjects

Twenty

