6.6 Prior and Concomitant Therapy

Study participants will stop other first-generation antihistamines and start cetirizine (Zyrtec) 10 mg 1 tablet bid two weeks prior to the first dose of Nucala, and continue throughout the duration of the study.

Epinephrine auto-injectors will be dispensed to the participants on baseline visit and must be carried at all times.

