7.1 Visit 1 (Week -2/Screening & Enrollment)

- a) Informed Consent
- b) History & Physical
- c) 4 mm punch skin biopsy (**4 mm punch skin biopsy within 6 months prior to visit 1 is acceptable**)
- d) UCT score assessment
- e) Review and distribute UAS log book
- f) Blood work: CBC with differential, serum IgE level, chronic urticaria index, IgE Fc receptor antibody functional assay (**Blood work within 6 months prior to visit 1 is acceptable**)
- g) Urine Pregnancy Test (if applicable)
- h) Photograph Biopsy site (**Photograph Biopsy site within 6 months prior to visit 1 is acceptable**)
- i) Dispense cetirizine (Zyrtec) 10 mg PO BID (#140 tablets)

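### Cetirizine and other antihistamine intake is not among the data the plan lists, so a change between the baseline week and week 10 could mimic or mask a mepolizumab effect without being seen

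*Combined protocol and SAP*

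**What the plan says.** Section 3.1 fixes the background treatment: "cetirizine 10 mg PO BID which will be continued throughout the study duration". Section 6.6 agrees that patients start it before the first injection "and continue throughout the duration of the study".

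Section 6.5, the compliance section, is one sentence: "Study participants will receive Nucala subcutaneous injection at each follow-up visit". It does not mention cetirizine.

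On patient records, section 3.1 says: "Patients will be provided with a log book to track daily urticaria signs and symptoms in a standardized manner for UAS scoring". Section 4.2 defines the daily entries as a wheal count and an itch grade.

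Cetirizine supply appears once, at Visit 1 (section 7.1): "Dispense cetirizine (Zyrtec) 10 mg PO BID (#140 tablets". The schedule table at the end of section 7 marks cetirizine dispensing at week -2 and at no later visit.

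Section 6.3 states that there is no placebo arm. Sections 4.2 and 8.1 make the primary analysis a paired comparison of UAS7 before and after treatment.

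**The concern.** With no control arm, anything that differs between the baseline week and week 10 enters the estimated effect. The plan deals with one such factor, background antihistamine, by fixing the regimen. Cetirizine is taken at home, yet compliance monitoring covers only the injection that staff give.

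If antihistamine intake is higher in week 10 than at baseline, UAS7 may fall with no mepolizumab effect. If it is lower, a real effect may be hidden. Daily intake cannot be reliably reconstructed afterwards, so neither case could be examined once the data are in.

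**Working it through.** **1. Where intake could have been recorded**

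| Place | What it covers |
|---|---|
| 6.5 Compliance | Clinic injection only |
| 3.1 and 4.2, log book/diary | "log book to track daily urticaria signs and symptoms"; scored as wheals and itch |
| 4.5 Source data | UCT, ISS, UAS7, adverse events, counselling; laboratory and biopsy results elsewhere |
| 7.2 to 7.6 and schedule, weeks 0 to 10 | No medication review, tablet count or tablet return |
| 6.9.3 Reconciliation | Study drug, which 6.1 describes as Nucala |
| 5.4.1 Noncompliance | General withdrawal rule; no way of measuring cetirizine intake |

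**2. Tablet supply against duration**

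- Supply: 140 / 2 per day = 70 days.
- Visit 1 at week -2 (7.1): to week 10 is 12 × 7 = 84 days, or 168 tablets. The shortfall is 28 tablets (14 days), so supply ends at week 8. With the ±5-day window at week 10 the need is 158 to 178 tablets.
- Week 0 at enrolment plus 7 days (3.1): 11 × 7 = 77 days, or 154 tablets. The shortfall is 14 tablets (7 days), so supply ends at week 9.

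If the week-10 score uses the seven days before that visit, the dispensed supply taken as prescribed does not cover the endpoint week on either timing.

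**3. The plan's own power figure**

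Section 8.1 states 99% power for 10 points with N = 20 at 5%. It gives no SD of the paired difference and does not say whether the test is one- or two-sided, so the figure cannot be reproduced directly. Solving a two-sided paired t-test (19 df, critical value 2.093) for 99% gives an SD of 9.88. The noncentrality is 10 × √20 / 9.88 = 4.53 and the power is 0.99. This SD is used below as an assumption.

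**4. Intake higher at week 10, no drug effect**

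The documents give no effect of cetirizine on UAS7. Assume that a patient whose intake changes shifts by 1 point of daily UAS, which is 1 × 7 = 7 UAS7 points. If 10%, 25% or 50% of patients change in the same direction, the mean shift b is 7 × 0.10 = 0.7, 7 × 0.25 = 1.75 or 7 × 0.50 = 3.5.

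The probability of a significant result in the drug's favour is P(T > 2.093), where T is noncentral t with 19 df and noncentrality b√20/SD. The SD is held fixed.

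| Mean fall b | SD 8 | SD 9.88 | SD 12 |
|---|---|---|---|
| 0 | 0.025 | 0.025 | 0.025 |
| 0.7 | 0.06 | 0.05 | 0.04 |
| 1.75 | 0.15 | 0.11 | 0.09 |
| 3.5 | 0.46 | 0.32 | 0.24 |

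Halving the assumed daily shift to 0.5 point halves each mean shift. Half the patients changing would then give 1.75 points, and 0.11 at SD 9.88.

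**5. Intake lower at week 10, true drug effect 10 points, SD 9.88**

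- Lose 3 points: noncentrality 7 × √20 / 9.88 = 3.17, power 0.85.
- Lose 5 points: noncentrality 5 × √20 / 9.88 = 2.26, power 0.57.

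On the 1-point-a-day scale these losses need 3/7 = 43% and 5/7 = 71% of patients to change. A supply that runs out for everyone could reach that many.

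**The case against.** The strongest objection is eligibility. Section 5.1 admits only patients who have not responded to oral antihistamines. If the drug does little for them, changes in intake move UAS7 little, and a 1-point shift on every day of the week is generous. This stands as a limit on size. It does not remove the point: non-response has no stated dose or threshold, and the sponsor still chose to standardise cetirizine.

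The CRF and log book pages are not in the documents, so the gap is inferred from the lists and descriptions. Section 6.5 sits under the study-drug heading, which explains its focus on Nucala. The withdrawal rule in 5.4.1 covers noncompliance in general. All of this is fair, but none of it supplies a measurement of cetirizine intake.

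A reader might go further in four ways that the documents do not support:

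- **That a change in intake would be read as drug benefit.** The direction is open, and the one concrete lead, the tablet supply, points towards masking.
- **That patients adjust cetirizine to their symptoms.** The protocol prescribes a fixed twice-daily dose and says nothing about such behaviour. It is plausible, but an assumption.
- **That patients will be without cetirizine in week 10.** No later dispensing is scheduled, but the text does not rule out resupply or self-purchase.
- **That analysing only patients with equal intake in both weeks would remove the bias.** Intake may itself depend on response, so this selects on post-baseline behaviour, in at most 20 patients.

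**Conclusion.** The point holds as a two-directional gap in measurement. The before/after contrast assumes a constant antihistamine background, and no listed item would show whether it was constant. The supply arithmetic gives a documented reason to doubt it in the endpoint week.

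The size is unknown. On the assumed shifts and the back-solved SD, the chance of a false positive in the drug's favour ranges from about 0.05, close to the nominal 0.025, to 0.32 if half the patients change the same way. Offsetting changes between patients would shrink the net shift. Neither the shifts nor the SD comes from the documents.

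Recording intake makes a change visible. It does not remove confounding from a single-arm design. For an exploratory study this is a cheap improvement that should be made, not a flaw that invalidates the plan.

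**What to change.** - **3.1 and 4.2:** add one daily line to the log book: cetirizine tablets taken, and any other antihistamine taken (yes/no, name).
- **4.5 and 6.5:** list this item as source data and as the measure of background compliance.
- **8.2:** report intake in the baseline week and the week-10 week beside the UAS7 change, showing both increases and decreases. If a same-intake subgroup is shown at all, label it descriptive only.
- **Tablet counts** are optional. Counts at two-weekly visits with ±5-day windows cannot isolate the seven-day scoring weeks; the diary line can.
- **Reconcile:** the 140-tablet supply in 7.1 with the stated duration; 3.1 ("Patients will discontinue all anti-histamines") with 6.6 ("Study participants will stop other first-generation antihistamines") on which drugs stop; and the lead-in before baseline, seven days in 3.1 against two weeks in 6.6 and 7.1. Which reading is right is for the sponsor to decide.

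The cost is one diary line, one data item and one descriptive table, with slightly more burden on patients. Sample size, dosing and visits do not change.

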6.6 Prior and Concomitant Therapy

Study participants will stop other first-generation antihistamines and start cetirizine (Zyrtec) 10 mg 1 tablet bid two weeks prior to the first dose of Nucala, and continue throughout the duration of the study.

Epinephrine auto-injectors will be dispensed to the participants on baseline visit and must be carried at all times.

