4.2 Primary Study Endpoints

The primary endpoint of the study will be the mean UAS7 reduction before and after 10 weeks of treatment with mepolizumab. The urticaria activity score (UAS) is a widely used CSU measure for daily pruritus and number of hives, which summed over a week, gives a UAS7 score. Study participants will document their CSU symptoms using a diary during the 10 week study period using the following daily scoring for a) the number of wheals [none (=0 points), <10 (=1 point), 10–50 (=2 points), or >50 per day (=3 points)], and b) the intensity of pruritus [none (=0 points), mild (=1 point), moderate (=2 points), severe (=3 points)]. The daily UAS score is summed over a week to calculate the UAS7 score (range: 0–42).

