5.1 Inclusion Criteria

Informed subject consent will be obtained from those patients meeting the following inclusion criteria:

- Male and female patients 18 years or older.
- Clinical and/or histopathological diagnosis of conventional CSU
- Unresponsive to oral antihistamine therapy
- Good general health as confirmed by medical history
- Patients who are willing and capable of cooperating to the extent and degree required by the protocol; and
- Patients who read and sign an approved informed consent for this study

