5.2 Exclusion Criteria

Patients are to be excluded based on the following criteria:

- Vulnerable study population
- If you are female and pregnant
- Biopsy proven neutrophilic rich urticarial which is unlikely to respond to mepolizumab given the postulated therapeutic mechanism
- Known history of adverse reaction to mepolizumab (Nucala)

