7.2 Visit 2 (Week 0± 5 days Baseline)

- a) UAS7 score assessment
- b) ISS score assessment
- c) Nucala 200mg injection
- d) Dispense epinephrine auto-injector

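### Only antihistamines are standardised: no rule keeps corticosteroids, immunosuppressants or biologics for urticaria absent or stable across the two UAS7 weeks, which leaves an avoidable risk of bias in a single-arm change

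*Combined protocol and SAP*

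**What the plan says.** The primary endpoint is a within-patient change: "The primary endpoint of the study will be the mean UAS7 reduction before and after 10 weeks of treatment with mepolizumab" (4.2). Section 6.3 confirms that there is no placebo arm.

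Background treatment is addressed in two places. Section 6.6 says "Study participants will stop other first-generation antihistamines and start cetirizine (Zyrtec) 10 mg 1 tablet bid", starting two weeks before the first dose. Section 3.1 is wider within the same class: "Patients will discontinue all anti-histamines and start cetirizine 10 mg PO BID which will be continued throughout the study duration". Neither mentions any other urticaria treatment.

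Eligibility requires "Unresponsive to oral antihistamine therapy" (5.1). Section 5.2 lists four exclusions: vulnerable population, pregnancy, neutrophil-rich urticaria on biopsy, and "Known history of adverse reaction to mepolizumab (Nucala". None concerns treatment before or at entry.

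Item 4 of section 1.6 says that a corticosteroid reduction, where appropriate, is to be gradual and supervised by a physician. It does not say when, relative to the UAS7 weeks, a reduction may happen.

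**The concern.** By putting everyone on the same cetirizine dose, the plan accepts that background treatment should be held constant while UAS7 is compared over time. It then stops at one drug class. Patients who have not responded to antihistamines are those in whom another systemic treatment is plausible, either current or recently stopped.

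In a controlled trial, such changes would occur in both arms and largely offset each other. Here there is no comparator, so any change between the baseline week and week 10 goes straight into the estimate. A taper, or a drug wearing off after being stopped before entry, pushes UAS7 up and hides a benefit. Added or increased treatment pushes UAS7 down and mimics one. Masking matters particularly here: section 1.5 justifies the more frequent dosing by the wish not to miss a therapeutic effect.

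**Working it through.** **Step 1. Does another provision close the gap?**

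| Provision | What it covers | What it leaves open |
|---|---|---|
| 1.6 item 2, severe-asthma exclusion | High-dose inhaled or systemic steroids for severe asthma | Steroids taken for urticaria; it is not repeated in 5.2 |
| 5.4.1, treatment failure | Withdrawal, at the investigator's judgment, when other treatment is needed | Treatment present at entry, carry-over, tapering in a patient who stays in |
| 8.3, sensitivity analysis | Excludes patients who withdrew | Patients who changed treatment and stayed |

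All three help in part. None requires non-antihistamine treatment to be absent or stable.

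**Step 2. The plan's own power figure.** Section 8.1 gives n = 20, a paired t-test at 5%, a 10-point change and 99% power. It gives no SD of the change and no sidedness. Assume a two-sided test: df = 19, critical value 2.093.

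Power = P(T > 2.093), where T is noncentral t with 19 df and noncentrality δ = 10 × √20 / SD. Power of 0.99 needs δ = 4.525, so SD = 10 × 4.472 / 4.525 = 9.88. A one-sided test would imply 10.84. The 99% therefore cannot be checked directly; it holds if the SD is about 9.88.

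**Step 3. Illustration of size.** The documents give neither the frequency nor the effect of background treatment, so the shifts below are assumptions. Exactly k of 20 patients shift by c points and all stay in the study.

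- Mean shift = k × c / 20 when all shift the same way.
- Expected SD of the change = √(9.88² + (20/19) × p(1 − p) × c²), with p = k/20. For k = 4, c = 10: √(97.7 + 16.8) = 10.70. For k = 4, c = 15: √(97.7 + 37.9) = 11.64.

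Rejection rates by simulation of the two-sided paired t-test:

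| Assumed shift | Mean shift | Power at a true 10-point change, if masking | Rejection with no true effect, if inflating |
|---|---|---|---|
| None | 0 | 99.0% | 5.0% |
| 1 patient × 5 points | 1/20 × 5 = 0.25 | 98.6% | 5.0% |
| 3 against 1 × 10 points | (3 − 1)/20 × 10 = 1.0 | 95.5% | 4.9% |
| 4 patients × 10 points | 4/20 × 10 = 2.0 | 90% | 11% |
| 4 patients × 15 points | 4/20 × 15 = 3.0 | 75% | 16% |

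Small or opposing shifts matter little. Several large shifts in one direction matter. The documents do not say which case applies.

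**Step 4. Can analysis repair it afterwards?** Not cleanly. Patients who add treatment may be those doing badly, so dropping them favours the drug. With no true effect and SD 9.88, dropping the 4 worst changes of 20 raises the mean improvement by 3.3 points (an upper bound); dropping 4 at random from the worse half raises it by 1.9. The control has to be in the design.

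**The case against.** The strongest case against is about weight. This is a 20-patient, open-label exploratory study without a control arm; natural fluctuation and expectation will affect the change whatever is done about background drugs. No passage shows that any participant takes a corticosteroid, immunosuppressant or biologic. Material harm appears only when about a fifth of patients all shift the same way by 10 points or more. The inflating direction also needs patients to receive other treatment and stay in, whereas 5.4.1 lets the investigator withdraw them. All of this stands, and it limits the point to a risk. It does not remove the gap: withdrawal is discretionary and does not reach treatment at entry, carry-over or tapering, which are the masking routes.

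Two stronger readings are tempting and should not be drawn.

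- A reader might infer from item 4 of section 1.6 that steroid tapering is planned or expected. It is one entry in a list of drug risks and says only how a reduction would be done. Its relevance is that it leaves the timing open.
- A reader might compute that the run-in gives too short a washout, perhaps none. Section 7 has "Visit 1 (Week -2/Screening & Enrollment" and "Visit 2 (Week 0± 5 days Baseline", about two weeks apart, while 3.1 says "At week 0 (enrollment visit +7 days), baseline UAS7 and ISS score will be assessed", which leaves no days before a seven-day baseline week. But no passage tells patients to stop a non-antihistamine drug at Visit 1, so these intervals describe a stop that the protocol never orders. The one-week versus two-week mismatch is a separate inconsistency and is not evidence here.

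**Conclusion.** The concern holds as an avoidable design risk. The textual gap is clear: 3.1 and 6.6 standardise antihistamines only, 5.2 has no treatment criterion, and 1.6 item 4 does not tie corticosteroid reduction to the UAS7 weeks. The likelier harm is masking; inflation is partly limited by 5.4.1.

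The size is unknown. The figures of 75% to 98.6% power and 5% to 16% false positives rest on assumed shifts, a two-sided test and an SD back-solved from the stated power. They show what could happen and are not estimates for this trial. A reader might conclude that the UAS7 result will be biased; the documents do not support that, because they give no frequency, direction or size of background-treatment change. The gap is still worth closing before enrolment, because wording can close it then and analysis cannot cleanly do so later.

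**What to change.** 1. In 5.2 and 6.6, require that non-antihistamine systemic urticaria treatments (systemic corticosteroids, immunosuppressants, biologics) are either absent, with washout completed before the baseline UAS7 week starts, or continued at an unchanged dose from before that week through the week-10 visit. Fix the washout interval for each agent before enrolment; the documents give no basis for choosing these, so the sponsor must set them.
2. In 1.6 item 4, allow no elective corticosteroid reduction between the baseline UAS7 week and the week-10 UAS7. Reductions needed for safety stay allowed and are recorded.

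**Cost.** Protocol wording only; no extra arm or larger sample. Some candidates become ineligible or wait for washout. Their number cannot be sized, because the 188 patients in 5.3 are all CSU patients seen in 2014, not only those unresponsive to antihistamines. Patients kept on a stable steroid dose may have an elective taper delayed by about 10 weeks; those for whom that is unacceptable should not be enrolled. The rule reduces this one risk. It does not make an uncontrolled, open-label change attributable to mepolizumab.

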6.7 Packaging

Each single-dose vial delivers mepolizumab 100 mg, polysorbate 80 (0.67 mg), sodium phosphate dibasic heptahydrate (7.14 mg), and sucrose (160 mg), with a pH of 7.0.

A quantity of 200 Nucala (100 mg) vials will be shipped to the Mayo Clinic research pharmacy in Florida and then labeled upon receipt with statement “Caution: New Drug Limited by Federal law for investigational use.”

6.8 Masking/Blinding of Study

This is an open-label pilot investigation. Masking and blinding procedures are not applicable. Qualitative and quantitative evaluations of response to treatment will be recorded.

6.9 Receiving, Storage, Dispensing and Return

6.9.1 Receipt of Drug Supplies

The drug will be shipped by GlaxoSmithKline to the Mayo Clinic research pharmacy in Florida. The pharmacy site will receive 200 100-mg vials of Nucala (mepolizumab). Upon receipt, an inventory will be performed and a drug receipt log filled out by the person accepting the shipment. Designated study staff will count and verify that the shipment contains all the items noted in the shipping invoice. Any discrepancies, damaged or unusable study drug in a given shipment will be documented in the study files. The sponsor-investigator must be notified immediately of any discrepancies, damaged or unusable products that are received.

